## 6. Efficacy Variables

### 6.1. Primary Efficacy Variable

#### **SBPday**

The primary efficacy variable will be SBPday. Appendix A of this SAP outlines the methodology for obtaining this variable.

### 6.2. Secondary Efficacy Variables

#### **Body Weight**

The measurement of the change in body weight from baseline to the end of treatment will serve as an indirect measure of renal function and is the first secondary efficacy endpoint analyzed in the serial gatekeeping strategy. Body weight will be measured while the subject is wearing only underwear and a light gown.

#### **SBP24h and DBP24hr**

The next secondary efficacy endpoints (after change in body weight) used in the serial gatekeeping strategy are the change in SBP24h from the baseline to the end of treatment and the change in DBP24h from baseline to the end of treatment, respectively. Appendix A of this SAP outlines the methodology for obtaining these variables.

For efficacy analyses, the validity of ABPM measurements will be based on valid daytime measurements. The impact of defining valid SBP24h and DBP24h measurements based on valid daytime readings is that some invalid measurements with respect to the 24-hour period (i.e., not meeting criterion d or e listed in Section 1.3.1) will remain in the analysis of the 24-hour variables. Sensitivity analyses excluding measurements that had an entry of valid for day validity and an entry of invalid for night or 24h validity will be conducted to verify that the inclusion of the invalid measurements does not impact the secondary efficacy conclusions. Details of the Sensitivity analyses are described in Section 7.10.

### **Renal function**

The final secondary efficacy endpoint in the serial gatekeeping strategy is the change in creatinine clearance from baseline to end of treatment. Creatinine clearance will be estimated by the Cockcroft-Gault equation as follows:

$$\text{Estimated creatinine clearance} = \frac{(140 - \text{age}) \times \text{body weight (kg)}}{72 \times P_{Cr} \left( \frac{\text{mg}}{\text{dL}} \right)}$$

*Note: multiply by 0.85 for women*

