7.3 Renal Function

Renal function as measured by estimated creatinine clearance is a secondary efficacy assessment of this trial. Creatinine clearance will be estimated at the initial screening visit, Day 0, Day 7, and Day 14. Creatinine clearance will be estimated by the Cockcroft-Gault equation as follows:

$$\text{estimated creatinine clearance} = (140 - \text{age}) \times \text{body weight (kg)} / 72 \times P_{Cr} \text{ (mg/dL)}$$

multiply by 0.85 for women

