that the enhanced antihypertensive effect when celecoxib was added was not due to an increased amlodipine plasma concentration through some pharmacokinetic (PK) drug-drug interaction (DDI).

An alternative explanation for the antihypertensive synergistic effect may be found in the renal data. Specifically, although patients treated with amlodipine had improved renal function as evidenced by a decreased serum creatinine, there was a trend towards an even greater reduction in serum creatinine among patients treated with both amlodipine and celecoxib. Such an enhancement in renal function might be expected to improve BP control and thus, at least partially explains the synergistic antihypertensive effect. However, since this renal synergy did not reach statistical significance, confirmation would require future clinical investigations. Study No. KIT-302-03-02 was designed to confirm this effect.

Further evidence for a renal component in the synergistic antihypertensive effect can be identified in the adverse event (AE) tables. Specifically, patients treated with amlodipine had a nearly 16% reporting rate of peripheral oedema; such an adverse reaction has been a long-recognized side effect of amlodipine. However, among those patients receiving both amlodipine and celecoxib, the rate of reported peripheral oedema was nearly halved. Thus, it would appear possible that the addition of celecoxib to amlodipine is in some way acting as a diuretic, thereby preventing the peripheral oedema and thus, enhancing the antihypertensive effect. Since this indirect measure of renal synergy did not reach statistical significance, confirmation would require future clinical investigations. Study No. KIT-302-03-02 was designed to confirm this effect.

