**j. Hematology, serum chemistry, and urinalysis**

For the majority of the hematology, serum chemistry, and urinalysis tests, the comparisons of the safety population data among treatment arms using Chi-square, binomial, and logistic analyses for dichotomous variables (e.g., negative/positive) and ANCOVA for continuous variables will not be done due to the limited number of subjects. The exceptions are serum creatinine and blood urea nitrogen (BUN), where comparisons between treatment arms will be performed using an ANCOVA model with change from baseline to Day 14 as the dependent variable, treatment as the fixed effect, and baseline as the covariate.

The laboratory reference range for assigning low "L" flags to the creatinine clearance results differed for the Celerion, Belfast laboratory (>90 mL/min) versus the centralized laboratory used for the remaining sites (ACM Global Central Laboratories;  $\geq 60$  mL/min). The serum chemistry shift table analysis will be based on the laboratory assigned flags (i.e., no reassignment of the Celerion, Belfast laboratory flags based on the ACM laboratory reference range will be made). The main body of the clinical study report will note the difference in the creatinine clearance reference range for the two

laboratories and will note by treatment group any cases where a Celerion, Belfast low creatinine clearance value would be reassigned as Normal if the  $\geq 60$  mL/min criterion was used.

Documentation of the differing creatinine clearance reference ranges for ACM and Celerion, Belfast is included in Appendix 16.1.10 of the clinical study report and in the individual subject laboratory reports that are included with the consolidated case report form PDF files, copies of which are included in the Trial Master File.

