2. A two-sample t-test for superiority will be used to test the one-sided hypothesis that treatment with amlodipine tablets (10 mg) and celecoxib capsules (200 mg) given together (arm 1) lowers SBP24h to a greater degree than amlodipine tablets (10 mg) given alone (with matched celecoxib placebo) (arm 2).

$$H_0: \Delta SBP_{24h,1} - \Delta SBP_{24h,2} = 0$$

$$H_1: \Delta SBP_{24h,1} - \Delta SBP_{24h,2} > 0$$

Where  $\Delta SBP_{24h,1}$  is the change, for subjects in arm 1, in SBP24h from the baseline ABPM measurement to the post-treatment ABPM measurement.

$\Delta SBP_{24h,2}$  is the change, for subjects in arm 2, in SBP24h from the baseline ABPM measurement to the post-treatment ABPM measurement.

3. A two-sample t-test for superiority will be used to test the one-sided hypothesis that treatment with amlodipine tablets (10 mg) and celecoxib capsules (200 mg) given together (arm 1) lowers DBP24h to a greater degree than amlodipine tablets (10 mg) given alone (with matched celecoxib placebo) (arm 2).

$$H_0: \Delta DBP_{24h,1} - \Delta DBP_{24h,2} = 0$$

$$H_1: \Delta DBP_{24h,1} - \Delta DBP_{24h,2} > 0$$

Where  $\Delta DBP_{24h,1}$  is the change, for subjects in arm 1, in DBP24h from the baseline ABPM measurement to the post-treatment ABPM measurement.

$\Delta DBP_{24h,2}$  is the change, for subjects in arm 2, in DBP24h from the baseline ABPM measurement to the post-treatment ABPM measurement.

4. A two-sample t-test for superiority will be used to test the one-sided hypothesis that treatment with amlodipine tablets (10 mg) and celecoxib capsules (200 mg) given together (arm 1) improves creatinine clearance to a greater degree than amlodipine tablets (10 mg) given alone (with matched celecoxib placebo) (arm 2).

Note: an improvement in creatinine clearance is assumed to be an increase in creatinine clearance; therefore, a positive difference is an indication of improvement as shown in the following hypotheses.

$$H_0: \Delta CC_1 - \Delta CC_2 = 0$$

$$H_1: \Delta CC_1 - \Delta CC_2 > 0$$

Where  $\Delta CC_1$  is the change, for subjects in arm 1, in creatinine clearance from the baseline creatinine clearance to the post-treatment creatinine clearance.

$\Delta CC_2$  is the change, for subjects in arm 2, in creatinine clearance from the baseline creatinine clearance to the post-treatment creatinine clearance.

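### Does the unstated body weight in the Cockcroft-Gault creatinine clearance endpoint call for a change to the plan?

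*SAP*

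**What the plan says.** SAP 6.2 places the endpoint in the hierarchy: "The final secondary efficacy endpoint in the serial gatekeeping strategy is the change in creatinine clearance from baseline to end of treatment". Protocol 7.3 and SAP 6.2 give the equation as (140 − age) × body weight / (72 × plasma creatinine), times 0.85 for women. The weight term carries no visit label. Protocol 7.3 adds: "Creatinine clearance will be estimated at the initial screening visit, Day 0, Day 7, and Day 14". Protocol 7.2 schedules body weight at the same four visits. Protocol Appendix B treats the clearance calculation as part of the creatinine laboratory result, and SAP 6.4 gives clearance a double role as efficacy and safety variable. SAP 7.8 sets Day 0 pre-dose as baseline and Day 14 as endpoint for both weight and clearance. It tests whether arm 1 (amlodipine plus celecoxib) increases clearance more than arm 2 (amlodipine alone), noting that "an improvement in creatinine clearance is assumed to be an increase in creatinine clearance".

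Weight change is also the first secondary endpoint. SAP 6.2 says of it: "The measurement of the change in body weight from baseline to the end of treatment will serve as an indirect measure of renal function".

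SAP 1.1 gives two reasons to expect a renal difference in the combination arm. In the previous trial "there was a trend towards an even greater reduction in serum creatinine among patients treated with both amlodipine and celecoxib", and it appeared possible that "the addition of celecoxib to amlodipine is in some way acting as a diuretic, thereby preventing the peripheral oedema".

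**The concern.** The two effects in SAP 1.1 push this endpoint in opposite directions. A larger fall in creatinine raises estimated clearance. Less retained fluid lowers body weight, which lowers estimated clearance if the Day 14 weight is used. Under the sponsor's hypothesis, a lower arm 1 weight would then be favourable in the first secondary endpoint and unfavourable in the last. A true creatinine-driven gain could be partly hidden. If celecoxib instead caused fluid retention, clearance could rise in arm 1 with no change in creatinine. Two analysts working from the same data could also compute different values, one with Day 0 weight and one with Day 14 weight.

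**Working it through.** The plan states no effect size, SD or power for clearance, so there is no figure to reproduce. The check asks how far weight can move the endpoint.

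1. **Leverage of weight.** Clearance is proportional to weight, so 1 kg is 100/weight per cent: 1.82% at 55 kg (the entry minimum), 1.18% at 85 kg, 1.00% at 100 kg. For an assumed man of 60 years, 85 kg and 0.9 mg/dL, clearance is 80 × 85 / (72 × 0.9) = 104.94 mL/min, so 1 kg is 104.94/85 = 1.23 mL/min. Other assumed profiles give 0.77 (woman, 75 years, 1.0 mg/dL) to 1.54 (man, 40 years, 0.9 mg/dL).

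2. **Weight gap that the documents suggest.** Protocol section 1 gives oedema rates of 15.6% on amlodipine alone and 8.2% on the combination, a difference of 7.4 points. At an assumed 1 to 3 kg per case, the mean gap is 0.074 × 1 = 0.07 kg to 0.074 × 3 = 0.22 kg. SAP 1.1 itself qualifies this evidence: "Since this indirect measure of renal synergy did not reach statistical significance". For oedema alone to produce gaps of 0.5 and 1 kg would need 0.5/0.074 = 6.8 kg and 1/0.074 = 13.5 kg per excess case.

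3. **Worked subject.** If creatinine falls from 0.90 to 0.85 mg/dL, clearance rises by 6.17 mL/min at fixed weight, 5.89 if the subject is 0.22 kg lighter and 4.87 if 1 kg lighter. If arm 2 gains the fluid instead, the between-arm result is nearly the same.

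4. **Power, clearance test taken alone.** Assumptions: 105 × 3/7 = 45 per arm, one-sided 2.5%, SD of change 10 mL/min, non-central t with 88 df. A gain of 5.97 mL/min has 80% power at fixed weight. With a weight gap g, the gain becomes 5.97 − 1.23g:
   - 0.07 kg: 79%
   - 0.22 kg: 76% (75% to 78% for SD 8 to 15, with the gain reset to 80% power each time)
   - 0.5 kg: 71%
   - 1 kg: 60%

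   At the achieved 6:6:1 allocation (about 48 per arm) these change by 1 point or less.

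5. **Smaller creatinine effects.** The share cancelled grows as the creatinine effect shrinks. At an assumed 58 years, 80 kg and 0.9 mg/dL, a 1% extra creatinine fall is worth 1.02 mL/min, and a 1 kg gap (1.28 mL/min) more than cancels it. But 1.02 is far below the 5.97 mL/min needed for 80% power, so such an effect would go undetected with either weight.

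6. **Place in the hierarchy.** SBP24h must succeed before clearance is reached. If the earlier trial's daytime difference (10.6 − 8.8 = 1.8 mmHg, pooled SD 8.67) and night-time difference (10.5 − 6.4 = 4.1 mmHg, pooled SD 11.01) bracket it, that step alone has about 16% to 42% power at 45 per arm. Formal success on clearance depends far more on this than on the choice of weight.

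7. **What already separates the components.** SAP 7.8 compares weight change across arms by ANOVA. SAP 7.9 adds an ANCOVA of weight with between-arm differences and confidence intervals, and an ANCOVA of serum creatinine with arm 1 against arm 2 as its primary comparison. With age and weight held at Day 0, the only term in clearance that can change is creatinine, so a fixed-weight version would largely repeat the creatinine ANCOVA.

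**The case for a change.** The best argument for a change is reproducibility. SAP 1.2 promises the algorithms for data derivations. The SAP says that age and BMI are taken from the CRF as recorded and that orthostatic hypotension is recalculated, yet it is silent on clearance, a named efficacy endpoint. The result is to be reported whatever the hierarchy shows (SAP 1.3.18), clearance is also a safety variable, and a clarifying sentence would cost little. All of this is fair, and recording in the study report which weight and which source were used would be good practice.

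Three parts of the case are weaker. First, the bias is not reliably conservative. Protocol section 1 hypothesises that celecoxib prevents the fluid retention amlodipine causes, which implies less weight gain in arm 1 rather than an outright loss. The celecoxib label in Protocol Appendix G (5.5 and 12.2) describes fluid retention, which would push the other way. Even then, the null of equal change in clearance is tested correctly; the risk is attributing a weight effect to the kidney. Second, the two laboratories are not evidence of differing derivations. SAP 1.3.9 j says that the reference range for flagging low "creatinine clearance results differed for the Celerion, Belfast laboratory (>90 mL/min) versus the centralized laboratory used for the remaining sites"; it says nothing about weight. Third, fixing Day 0 weight is one defensible preference, and nothing in the documents suggests that it was intended.

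**Conclusion.** The plan leaves out a detail that analysts would fill sensibly: each visit's own weight, or the laboratory's reported value. On the visit-weight reading the clearance test is valid, and the separate weight and creatinine analyses show what drove any difference. The likely cost is about 1 to 4 points of power on the last secondary endpoint. That rests on an assumed 0.07 to 0.22 kg gap, an assumed SD of 10 mL/min and a one-sided 2.5% level; the documents give no weight change or clearance SD, so the true size is unknown. A gap of 1 kg would matter more (80% falling to 60%), but the oedema figures do not support one. SAP v4.0 was finalised after unblinding (SAP 1.5), so choosing the weight now could not strengthen the hierarchical test. It could only add a post hoc table that largely repeats the creatinine ANCOVA. No change to the plan follows.

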## **6.3. Exploratory and Other Efficacy Variables**

### **Exploratory Efficacy Variables**

Exploratory efficacy variables will include DBPday, SBPnight, and DBPnight, and two-sample t-tests to test one-side hypotheses of superiority for pairwise comparisons between treatment arms 1 and 2, 1 and 3, and 2 and 3 will be performed for each. Further, SBPday, SBP24h, and DBP24h will serve as exploratory efficacy variables for the two-sample t-tests to test one-side hypotheses of superiority for pairwise comparisons between treatment arms 1 and 3 and 2 and 3 (the comparison of treatment arms 1 and 2 for these endpoints are covered separately under the respective primary and secondary efficacy analyses). Appendix A of this SAP outlines the methodology for obtaining these variables.

For the efficacy analyses, the validity of ABPM measurements will be based on valid daytime measurements. The impact of defining valid SBPnight and DBPnight measurements based on valid daytime readings is that some invalid night-time readings (i.e., not meeting criterion d listed in Section 1.3.1) will remain in the analysis of night-time variables. Sensitivity analyses excluding measurements that had an entry of valid for day validity and an entry of invalid for night validity will be conducted to verify that inclusion of the invalid measurements does not impact the exploratory efficacy conclusions. Details of the Sensitivity analyses are described in Section 7.10. See Section 6.2 regarding the impact of defining valid SBP24h and DBP24h measurements based on valid daytime readings.

### **SBP and DBP at Amlodipine Peak and Trough**

Other efficacy variables will include SBP and DBP at the expected peak amlodipine concentration and at the trough amlodipine concentration at Day 6 and Day 13, and the difference of the values between Day 6 and Day 13. The peak and trough values will be taken from the ABPM measurements. See Section 7.10 for further definition of the peak and trough values.

## **6.4. Safety Variables**

Safety will be assessed primarily based on reported TEAEs. Clinically significant clinical laboratory abnormalities will be reported as AEs (i.e., as either PTAEs or TEAEs, depending on when they initiate or worsen).

### **PTAE**

Any untoward medical occurrence that initiates or worsens after completion of the Initial Screening Visit procedures and before administration of the first dose of study drugs will be recorded as a PTAE.

### **TEAE**

Any untoward medical occurrence that initiates or worsens after the first dose of study drugs and within 14 days of the last dose of study drugs will be recorded as a TEAE.

In case of missing or incomplete dates and times not allowing a direct allocation to either of the two categories of AEs, a worst-case allocation will be done according to the available parts of the onset and the end dates. The AE will be allocated to the first category allowed by the available data, according to the following order:

- TEAE
- PTAE.

### **SAE**

A SAE is any untoward medical occurrence that results in death, is life-threatening, requires inpatient hospitalization or prolongation of existing hospitalization, results in persistent or significant incapacity or substantial disruption of the ability to conduct normal life functions, is a congenital anomaly/birth defect, or is an important medical event that, based upon appropriate medical judgement, may jeopardize the subject and may require medical or surgical intervention to prevent one of the former outcomes (i.e., AE with seriousness not equal to '0' on AE CRF).

### **ADR**

An ADR is an AE with relatedness to Study Drug judged as an "Adverse Reaction" (i.e., an AE that is caused by the study drug) or a "Suspected Adverse Reaction" (i.e., an AE for which there is a reasonable possibility that the study drug caused the AE) [i.e., an AE with relatedness to study drug not equal to 'unrelated' on AE CRF].

### **Oedema events**

An oedema event is any TEAE with a PT of oedema, oedema peripheral, peripheral swelling, swelling, or joint swelling.

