The oral administration of 10 mg amlodipine besylate and 200 mg celecoxib, either individually (i.e., with a matched placebo) or in combination once daily for 14 days in adult subjects with newly diagnosed hypertension who required pharmacological therapy was well tolerated. No deaths or serious adverse events (SAEs) were reported in Study No. KIT-302-03-01. Of the AEs that were considered to be related to the study drugs (i.e., assigned as either a suspected adverse reaction or adverse reaction by the Investigator), all were mild in severity, except for a single incidence of headache that was moderate in severity. Further, all of these AEs fully resolved.

Study No. KIT-302-03-01 also included the collection of PK blood samples at the end of the study (i.e., steady state; Day 14) in a subset of the trial population to evaluate for drug-drug interactions. The analyses showed that amlodipine had no statistically significant effect on the plasma levels of celecoxib. However, celecoxib reduced the plasma levels of amlodipine by approximately a third ($p < 0.001$). The mechanism for the enhancement in efficacy (lowering of BP) and trend towards improved renal function despite the reduction in the plasma concentration of amlodipine is currently unknown. Kitov hypothesizes that celecoxib prevents the fluid retention amlodipine causes (it acts in a manner similar to a diuretic) as evidenced by the reduced rate of oedema reported in patients receiving the combination therapy in the trial (8.2%) as opposed to those receiving amlodipine monotherapy (15.6%). Such a diuretic type effect would be expected to lower BP.

For further details regarding Study No. KIT-302-03-01 and the bioavailability studies, please refer to the most current version of the Investigator's Brochure (IB) for KIT-302.

This study will be performed in compliance with the current ICH guidelines for GCP and all applicable regulatory requirements.

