14.2 Rheumatoid Arthritis

CELEBREX has demonstrated significant reduction in joint tenderness/pain and joint swelling compared to placebo. CELEBREX was evaluated for treatment of the signs and symptoms of RA in placebo- and active-controlled clinical trials of up to 24 weeks in duration. CELEBREX was shown to be superior to placebo in these studies, using the ACR20 Responder Index, a composite of clinical, laboratory, and functional measures in RA. CELEBREX doses of 100 mg twice daily and 200 mg twice daily were similar in effectiveness and both were comparable to naproxen 500 mg twice daily.

Although CELEBREX 100 mg twice daily and 200 mg twice daily provided similar overall effectiveness, some patients derived additional benefit from the 200 mg twice daily dose. Doses of 400 mg twice daily provided no additional benefit above that seen with 100-200 mg twice daily.

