**d. Unexpected adverse event (UAE)**

A tabulation of treatment-emergent UAEs (defined in Section 6.4) will be added. The summary will include the number of events, as well as the number and percentage of subjects. Subjects will be counted once per category [specific system organ class (SOC) or PT], regardless of the number of events that may have occurred for that patient in that category. The tabulation will be based on the respective **Principal Investigator (PI) assignments** of expectedness. A statistical evaluation of the rate of treatment-emergent UAEs among treatment arms using a Chi-square test or Fisher's exact test (if more than 20% of the cells in a contingency table had expected counts less than 5) will be performed.

As with the prior trial (KIT-302-03-01), there are several TEAEs designated as unexpected by one or more PIs for one or more subjects that the Sponsor considered as expected based on the product labelings for the study drugs, including dyspepsia, flatulence, vomiting, chest pain, pain (lower body pain), thirst, nasopharyngitis (cold symptoms), pharyngitis, sinusitis, alanine aminotransferase increased, increased appetite, arthralgia, back pain, joint swelling (swelling of knee), dizziness, headache, cough, epistaxis, dry skin, purpura, and rash.

Further, there were several TEAEs designated as expected by one or more PIs for one or more subjects that the Sponsor considered as unexpected as they were not listed in the product labelings for the study drugs and were not listed as expected AEs in the protocol, including toothache, seasonal allergy (hayfever symptoms), urinary tract infection, plantar fasciitis, dysphoria, epididymal cyst, blister, pigmentation disorder, feeling cold, and peripheral coldness. It should be noted that in the prior study (KIT-302-03-01), the Sponsor assigned pollakiuria as an unexpected event in error. Micturition frequency is listed in the labelings for both study drugs. As such, the Sponsor considers the pollakiuria events in this study and the prior study as expected.

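### The oedema comparison counts every joint-swelling event, at least one of which was a swollen knee, and no planned test leaves such events out

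*SAP*

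**What the plan says.** SAP 6.4 defines the variable: "An oedema event is any TEAE with a PT of oedema, oedema peripheral, peripheral swelling, swelling, or joint swelling". SAP 1.3.9a and 7.9 use the same five preferred terms. None of the three places restricts joint swelling by site, cause or reported term.

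Two tests use the composite, both comparing arm 1 with arm 2: an exact logistic regression reporting the odds ratio, and a Fisher test of on-treatment and post-treatment events. SAP 7.3 sets two-sided 0.05 for safety tests.

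SAP 1.3.9d lists adverse events in this trial that investigators called unexpected and the sponsor considered expected. The list includes "arthralgia, back pain, joint swelling (swelling of knee), dizziness, headache".

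On interpretation, protocol section 1 gives the prior study's oedema rates, 8.2% on the combination and 15.6% on amlodipine alone, as evidence that celecoxib prevents fluid retention. SAP 1.1 describes the prior signal as peripheral oedema and infers that possibly "the addition of celecoxib to amlodipine is in some way acting as a diuretic". It adds: "Since this indirect measure of renal synergy did not reach statistical significance, confirmation would require future clinical investigations". Its next sentence says that the present study was designed to confirm the effect.

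**The concern.** A comparison offered as confirmation of less fluid retention should count fluid retention. Knee swelling is a joint event. Once it is counted as oedema, part of any difference between the arms may have nothing to do with fluid.

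Celecoxib is also an anti-inflammatory drug, so the added events need not be neutral noise. Its label, in protocol Appendix G, says for rheumatoid arthritis: "CELEBREX has demonstrated significant reduction in joint tenderness/pain and joint swelling compared to placebo". A joint effect could in principle be read as a fluid effect.

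What is at stake is the mechanistic reading of the oedema result. The primary endpoint and the secondary testing hierarchy do not depend on it.

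**Working it through.** **1. The passages side by side.** By SAP 6.4, any joint-swelling event is an oedema event. By SAP 1.3.9d, at least one joint-swelling event in this trial was a knee. So at least one knee event meets the oedema definition, provided it fell within the treatment-emergent window, which SAP 1.3.9d says of all the events it lists. No analysis in SAP 1.3.3, 1.3.9, 7.9 or 7.10 repeats the oedema tests without it.

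**2. Reproducing the documents' oedema figures.** The prior study randomised 152 subjects 1.5:1.5:1:1, so each amlodipine arm would hold about 152 × 1.5/5 = 45.6. For arm sizes from 40 to 52, the only whole-number counts that round to the stated rates are:

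- 4/49 = 8.2% (combination)
- 7/45 = 15.6% (amlodipine alone)

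These counts are inferred; the documents do not state them. The odds ratio is (4 × 38)/(45 × 7) = 152/315 = 0.48. The conditional exact estimate, which is what an exact logistic model with treatment alone gives, is 0.49 (95% CI 0.10 to 2.09). Fisher p = 0.34, which agrees with the SAP's statement that significance was not reached.

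**3. Effect of removing joint-only subjects.** The documents give no joint-swelling count for either trial, so this is a range on an assumed table, not an estimate. It takes 4/49 v 7/45 and supposes that some of those subjects had joint swelling as their only qualifying event.

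| Removed | Table | Odds ratio | Fisher p |
|---|---|---|---|
| none | 4/49 v 7/45 | 152/315 = 0.48 | 0.34 |
| 1 from amlodipine alone | 4/49 v 6/45 | (4 × 39)/(45 × 6) = 0.58 | 0.51 |
| 2 from amlodipine alone | 4/49 v 5/45 | (4 × 40)/(45 × 5) = 0.71 | 0.73 |
| 3 from amlodipine alone | 4/49 v 4/45 | (4 × 41)/(45 × 4) = 0.91 | 1.00 |
| 1 from combination | 3/49 v 7/45 | (3 × 38)/(46 × 7) = 0.35 | 0.19 |

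The conditional estimates differ from these by less than 0.01. The last row shows the opposite direction: if the joint event was in the combination arm, the composite understates the contrast.

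**4. The same point starting from no effect.** Assume 5/45 in each arm (45 per group is the figure in protocol H.4.1), so the odds ratio is 1.00. Adding 1, 2, 3 or 4 joint-only subjects to arm 2 alone gives conditional odds ratios of 0.81, 0.68, 0.58 and 0.50. Four such subjects would reproduce the apparent halving seen in the prior study.

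**5. Significance.** On the inferred table, one event does not change the test result: p stays far above 0.05 in every row of step 3. With four events in 49 on the combination, amlodipine alone would need 11 in 45 before p fell below 0.05 (p = 0.047). A single event decides the test only near that boundary. As a purely assumed example, with 48 per arm, 3 v 10 gives p = 0.070 and 3 v 11 gives p = 0.040.

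**The case against.** The case for leaving the plan alone has real force.

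- **The list is filtered.** SAP 1.3.9d introduces it with "As with the prior trial (KIT-302-03-01), there are several TEAEs designated as unexpected by one or more PIs for one or more subjects". An ankle event that an investigator marked as expected would not appear there, and leg or ankle swelling is named as an amlodipine side effect in the patient leaflet in Appendix F. The list shows that at least one joint-swelling event was a knee. It does not show that the term meant knee throughout, and ankle reports would be a sound reason to include the term.
- **Oedema is a safety variable.** It is not in the primary or secondary hierarchy. There the fluid and renal question rests on body weight and creatinine clearance. A broad term list suits a safety table.
- **Joint swelling will be visible.** SAP 7.9 tabulates oedema events by preferred term, and SAP 7.3 lists all case report form data.

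All three points stand. They lower the weight of the concern but leave one gap: both formal tests use the composite, and the odds ratio is what will be quoted.

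A reader might go further and infer that celecoxib's anti-inflammatory action will be scored as diuretic synergy. The documents do not support that. The label evidence is from rheumatoid arthritis. This trial enrolled subjects healthy apart from hypertension, excluded current NSAID users and treated for 14 days. The arm of the knee event is unknown, so the shift could go against the combination.

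A reader might also suspect that the term list was chosen after the results were seen. SAP v4.0 is dated after unblinding, but v3.0 was final before it, and nothing supplied shows whether v3.0 already held the list.

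**Conclusion.** The concern holds in a limited form. The oedema composite includes at least one event that is not peripheral oedema, and no planned test removes such events. That weakens the composite as evidence for or against a diuretic effect.

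In size, one to three joint-only subjects in the amlodipine-alone arm would move the odds ratio from 0.48 to between 0.58 and 0.91; one in the combination arm would move it to 0.35. This rests on two assumptions: counts like the inferred 4/49 v 7/45, and subjects whose only qualifying event was joint swelling. The true number and arm are not in the documents, so the direction cannot be stated. Exclusion of NSAID users suggests that joint events are few.

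No conclusion in the primary or secondary hierarchy is affected. It would go too far to say that the definition biases the trial towards the combination, or that one event will decide significance. Replacing the main definition is not warranted either: narrowing it after unblinding, in response to a known event, would be harder to defend than keeping it and adding an analysis.

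**What to change.** 1. Keep the five-term definition in SAP 6.4 as the stated safety analysis.
2. Add to SAP 7.9 a sensitivity run of both tests, the exact logistic regression and the on-/post-treatment Fisher test. Exclude joint-swelling events whose reported term is the knee or another single joint, and keep ankle, foot or leg terms. Have someone without access to the treatment code classify the reported terms, and record the classification before the rerun.
3. Label this analysis as post hoc, and report the number of reclassified events by arm.
4. State in SAP 1.3.9a when the five-term list was fixed, and in particular whether it stood in v3.0.
5. Do not cite the oedema result as support for a diuretic effect unless the two versions agree.

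The cost is a short review of a few reported terms, one rerun, and a post hoc label on the added analysis.
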